The guidelines pertaining to the management of critically ill adults with Coronavirus Disease 2019 [25] recommended administration of inhaled oxide as a rescue therapy for COVID-19 patients experiencing refractory hypoxemia [26]. Studies have proposed NO inhalation as an effective strategy for COVID-19 treatment [27], as SARS-CoV-2 modulates endogenous NO levels and availability upon entering host cells. It was demonstrated that NO can reduce SARS-CoV-2 viral load by 95% within 24 hours and over 99% within 72 hours [28]. Despite its theoretical plausibility and potential, the clinical evidence supporting the efficacy of NO in treating COVID-19-related pulmonary complications has primarily originated from observational studies [29, 30] or small trials [31], yielding inconsistent reported results. Recently, a phase II study demonstrated an improvement of  $\text{PaO}_2/\text{FIO}_2$  with high-dose NO (at 80ppm) at 48 hours compared with usual care in adults with acute hypoxic respiratory failure due to COVID-19 [32]. Although the clinically important hard outcomes did not differ, the exploratory results suggested that

inhaled NO leads to a steeper reduction in plasma viral load. In addition, at 80 ppm (relatively high dose), iNO was safe and well-tolerated.

The rationale for using iNO in treating surgical patients with COVID-19 is well established and lies in several key mechanisms. There are however very limited study exploring whether inhaled NO can improve postoperative lung function, especially in non-cardiac surgeries. Furthermore, no randomised controlled trial is available evaluating iNO in surgical patients with a history of recent SARS-CoV-2 infection [33].

INORDINATE is a single-center, randomized placebo controlled trial that aims to determine if intraoperative inhalation of 80 ppm NO will reduce the postoperative pulmonary complications in surgical patients with recent (within 7 weeks) SARS-CoV-2 infection.

The trial commenced in February 17, 2023 and the estimated timeline for completion of patient accrual was 12 months. Duration of participation for each patient is 30 days (last follow-up). The total study duration is estimated to be approximately 13 months. This statistical analysis plan details the planned analyses for INORDINATE to facilitate the transparency of data analyses. The trial protocol has previously been published [34].

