## STATISTICAL ANALYSIS PLAN

### Scope of the Analysis plan

This Statistical Analysis Plan (SAP) presents the analyses for the INORDINATE trial. The final manuscript will include follow-up data until leaving hospital for the trial and analyses will follow this SAP strictly.

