### **Stopping rules**

The patient's participation in the study is terminated if the patient (or trusted person) withdraws consent. In the event that the investigator temporarily or permanently discontinues participation in the study for any reason that would be in the best interest of the patient, particularly in the case of serious adverse events suspected to be related to the intervention strategy being tested, the patient remains in the analysis to respect the intention-to-treat principle, and his or her data are collected until 30 days after surgery (the final follow-up).

No interim analysis was planned, therefore there is no prespecified early termination rules for the study due to efficacy or futility.

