## **Missing and outlier Data**

We anticipate no missing values in the primary outcome and very low missing values in other variables if any. The demographics and chronic medical history will be filled on site, intraoperative data will be monitored and recorded in the operating rooms, and the follow-ups until discharge of hospital or deaths can be traced back in the electronic health records. If patients are lost during the 30-day follow-ups, no imputation will be conducted for outcomes. Data missing at baseline will be reported as such. In case where low missing rate (<5%) occurred with no trace-backs available, multiple imputation will be performed as a sensitivity analysis.

Outliers will be subject to a confirmation request to the investigators. In

case of confirmation, their value will not be modified, and will be taken into account as it is during the analysis.

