## **Primary Analysis**

The effects of inhaled NO on incidence of PPCs will be reported as number and percentages and estimated with risk ratio and 95% confidence intervals calculated with Wald's likelihood ratio approximation test and with Chi-squared or Fisher's exact test for hypothesis testing. The unadjusted analysis will estimate risk ratios with 95% confidence intervals by two-by-two table with the use of log-Normal approximation. In addition, the effect size will be expressed as risk differences (95% confidence intervals) with the number needed to treat as the reciprocal of the risk difference, rounded to the nearest integer. This will further be analysed as the generalised linear models (GLM) under binomial family with either log or logit link where appropriate. Odds ratios or relative risks together with 95% confidence intervals will be reported. Further adjustment on stratification variables such as ARISCAT index and time interval from infection to surgery will be made. The point estimates with 95% confidence intervals will be reported.

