## **Sensitivity Analysis**

The pre-specified sensitivity analysis will re-estimate the iNO effect on the primary outcome using GLM using a binomial distribution. Additional adjustment will be made for subgroups and any variables showing substantial imbalance across treatment arms at baseline. We assessed the balance of randomised groups on baseline and procedural characteristics using absolute standardised difference, defined as the absolute difference in means, mean ranks, or proportions divided by the pooled standard deviation. Baseline and procedural characteristics with absolute standardised difference  $>0.15$  ( $1.96 * \sqrt{1/330 + 1/330}$ ) were considered to be imbalanced and would be adjusted. The other way of exploring the potential imbalance across treatment arms will be achieved by constructing a logistic regression model to estimate the treatment effect and predictors of PPCs. Collinearity and overfitting will be assessed through Pearson's correlation tests and variation inflation factors. If outcome events are observed to be rare, a Poisson regression will be employed. Classic logistic regression will be performed with a consistent number of events, and the number of covariates in the model will be decided based on the number of outcomes. The ARISCAT score and operation duration score used as one randomization stratification will be treated as continuous variables, exploring their continuous impacts on the outcome.

Time-to-event (PPC) within the observation window (7 days and 30 days respectively) will be assessed using Kaplan-Meier curves and compared with log-rank tests. Per-protocol and as-treated analyses of PPCs will serve as sensitivity analyses. If a low missing rate (< 5%) in the primary outcome were presented, an extra sensitivity analyses with multiple imputations would be performed.

In addition to the standard analysis described above, the following analyses will be performed to test the robustness of the trial findings:

- (1) the count of positive component events within the composite will be assessed and groups will be compared using a Wilcoxon rank-sum test, and odds ratio with the 95% confidence interval will be assessed with a proportional odds logistic regression;
- (2) the effect of inhaled NO on each component will be analyzed using a GLM using Bonferroni correction for multiple comparisons with 99.37% Bonferroni-corrected confidence intervals reported ( $1 - 0.05/8 = 0.9937$ );

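### The SAP contradicts itself on follow-up and gives no censoring rule for time to PPC; if discharge is a censoring time, the Kaplan-Meier curves overstate PPC incidence

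*SAP*

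**What the plan says.** The SAP's Sensitivity Analysis section plans: "Time-to-event (PPC) within the observation window (7 days and 30 days respectively) will be assessed using Kaplan-Meier curves and compared with log-rank tests". No section defines the censoring times for this analysis, and no competing-risk method is named.

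Two statements point to data that end at discharge:
- Scope of the Analysis plan: "The final manuscript will include follow-up data until leaving hospital for the trial". The same sentence says that the analyses will keep strictly to the SAP.
- Missing and outlier Data: "the follow-ups until discharge of hospital or deaths can be traced back in the electronic health records".

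Three point to day 30:
- Background: "Duration of participation for each patient is 30 days (last follow-up".
- Stopping rules, for patients whom the investigator discontinues: "his or her data are collected until 30 days after surgery (the final follow-up".
- Missing and outlier Data: "If patients are lost during the 30-day follow-ups, no imputation will be conducted for outcomes".

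Table 2 also has a 30-day column, and 30-day mortality is a secondary endpoint.

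The Primary Analysis section treats the same event as a proportion: "The effects of inhaled NO on incidence of PPCs will be reported as number and percentages". The primary endpoint covers seven days. A 30-day window for PPC appears only in the time-to-event sentence.

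**The concern.** Kaplan-Meier estimates incidence correctly only if a censored patient has the same later hazard as those still at risk. Discharge does not meet that condition. Patients go home largely because they are free of complications, so those who remain in hospital are not representative of those who left. If discharge is a censoring time, the curve applies the hazard of the remaining inpatients to everyone who has gone home.

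The primary analysis keeps every patient in the denominator. The trial could then publish two different PPC rates for the same arm and window, with a 30-day curve that rests on a small group of long-stay patients. Two statisticians following this SAP could also produce different curves, one censoring at discharge and one keeping patients at risk to day 30.

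**Working it through.** **Figures in the plan.** The SAP gives no Kaplan-Meier incidence, length of stay or PPC onset time, so there is no figure of its own to reproduce. Its usable inputs, from Sample Size Consideration, are PPC rates of 30% (control) and 20% (NO), 330 patients per arm and 10% dropout. That leaves 330 × 0.9 = 297 evaluable per arm, and the standard error of a 30% rate is √(0.30 × 0.70 / 297) = 2.7 points.

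**Assumptions.** The in-hospital PPC hazard on day j is h_j = h_1·exp(−(j−1)/τ), with h_1 set so that 7-day incidence is 30% or 20%. Length of stay is log-normal with log-SD 0.6. No PPC occurs after discharge.

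**Formulas.** Let Y_j be the fraction in hospital and PPC-free at the start of day j, and b_j the probability of discharge that day.
- At risk: Y_(j+1) = Y_j(1 − h_j)(1 − b_j), with Y_1 = 1
- True incidence: Σ Y_j·h_j
- Kaplan-Meier with discharge censored: 1 − Π(1 − h_j)

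**One case in full: 30% control rate, τ = 4 days, median stay 5 days (h_1 = 0.1081).**

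| Day | h_j | Y_j | Y_j·h_j |
|---|---|---|---|
| 1 | 0.1081 | 1.0000 | 0.1081 |
| 2 | 0.0842 | 0.8886 | 0.0748 |
| 3 | 0.0656 | 0.7650 | 0.0502 |
| 4 | 0.0511 | 0.6126 | 0.0313 |
| 5 | 0.0398 | 0.4671 | 0.0186 |
| 6 | 0.0310 | 0.3477 | 0.0108 |
| 7 | 0.0241 | 0.2565 | 0.0062 |

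The last column sums to 0.300, the true incidence. The product of (1 − h_j) is 0.658, so one minus Kaplan-Meier is 34.2%, an excess of 4.2 points. By day 30 the true figure is 30.8% and the curve shows 39.6%, an excess of 8.8 points.

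**Excess in points at 30% incidence (day 7 / day 30).**

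| τ (days) | Median stay 5 d | 7 d | 10 d |
|---|---|---|---|
| 1.5 | 1.2 / 1.4 | 0.5 / 0.7 | 0.2 / 0.3 |
| 2.5 | 2.7 / 4.0 | 1.3 / 2.3 | 0.5 / 1.1 |
| 4 | 4.2 / 8.8 | 2.1 / 5.6 | 0.8 / 3.2 |
| 7 | 5.7 / 17.8 | 2.8 / 12.7 | 1.1 / 8.3 |

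At 20% incidence the same grid gives 0.1 to 4.1 points at day 7 and 0.2 to 13.5 at day 30. A median stay of 3 days with τ = 7 raises the 30% case to 13.0 and 27.6.

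**Late PPC.** Simulations with log-normal onset (median 2.5 or 3 days) and the same three median stays added in-hospital PPC among patients staying beyond day 8. The day-30 excess was about 0.2 to 6 points with none, 2 to 9 with 2%, 5 to 13 with 5%, and 8 to 23 with 10%. Taken with a further simulation of this type, the range is about 0.5 to 7 points at day 7 and 0.5 to 24 at day 30. The lowest cells above fall slightly under that.

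**Controls on the mechanism.** With status known to day 30 for everyone, the discharge effect is zero. If discharge is unrelated to PPC risk, the day-30 difference is −2.5 to +0.4 points. Censoring deaths alone, at 1% to 5% 30-day mortality, adds 0.1 point or less.

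**Log-rank test.** Simulated with 297 per arm, 30% against 20%, 800 replicates, and median stays of 5, 7 and 10 days. Rejection with discharge censored, against follow-up of everyone, was 78/79%, 81/81% and 81/81% at day 7, and 76/76%, 77/77% and 72/72% at day 30. Under the null with equal stay it was 4% to 6% either way. With stay 15% shorter in one arm, the only visible change was at median 5 days, about 8% against 6%.

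**The case against.** Three stronger readings are tempting, and the document does not support them.

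A reader might infer that the SAP's follow-up ends at discharge and that patients are therefore censored as they go home. No section says that discharge is a censoring time. Background, Stopping rules, Table 2 and the sentence on loss during 30-day follow-up all point to contact after discharge. If that contact records PPC status, the curves agree with the crude percentages apart from the small effect of death. What stands is a contradiction and a missing rule, with a bias that depends on how the contradiction is resolved.

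A reader might also attach a narrow figure to the day-30 bias, such as 9 to 20 points. That needs an assumed stay and an assumed rate of late PPC. Most cases with early onset (τ of 1.5 or 2.5 days) fall well below 9, and others exceed 20.

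Finally, a reader might conclude that the treatment comparison is compromised. A log-rank test with discharge censored still compares in-hospital cause-specific hazards, and the simulation shows almost no change when stay is equal between arms. The primary analysis is a two-by-two comparison at seven days and does not use these curves.

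The objection does not remove the point. The Scope section restricts the data to the hospital stay and binds the analysts to the SAP. Anyone who applies that sentence to a plain Kaplan-Meier analysis will censor at discharge.

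**Conclusion.** The point holds in conditional form. The SAP contradicts itself on whether data end at discharge or at day 30, and its time-to-PPC analysis has no rule for discharge or death. If PPC-free patients are censored at discharge, the curves overstate PPC incidence in every informative-discharge case examined. The sizes under Working rest on assumed stay and onset distributions and are not bounds. Many of the day-30 cases exceed the 2.7-point standard error of the control rate.

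The harm is confined to the height of the curves in one sensitivity analysis and to their disagreement with the primary percentages. The log-rank comparison becomes a concern mainly if NO changes length of stay.

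**What to change.** 1. Reconcile Scope of the Analysis plan with Background, Stopping rules and Missing and outlier Data, so that one end of follow-up applies and it is clear whether PPC status is collected after discharge.
2. In Sensitivity Analysis, replace the time-to-event sentence with wording such as: *Time to first PPC will be shown as cumulative incidence (Aalen-Johansen), with death without PPC as a competing event. Discharge is not a censoring event. PPC-free patients remain at risk until day 7 or day 30, or until last contact if lost to follow-up.*
3. If PPC status after discharge is not collected, treat discharge alive without PPC as a further competing event and label the result in-hospital PPC.
4. The log-rank test may stay, described as a comparison of cause-specific hazards. Gray's test is optional.

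The cost is a few sentences and a different R function. No visit is added if the 30-day contact already described is used.

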## **Secondary Analysis**

Secondary outcomes will be analyzed according to the intention-to-treat principle. Proportion of patients experiencing secondary endpoints including 30-day all-cause mortality, unplanned ICU admission, thrombotic events (including deep venous thrombosis and pulmonary embolism), non-pulmonary complications (including stroke, cardiac infarction, ventricular dysfunction, delirium, acute kidney injury, surgical revision for bleeding, hypotension/hypertension, arrhythmia, hyper-responsiveness) will be compared using Fisher's exact test or Chi-squared tests depending on incidence rate. Each component of the thrombotic events and non-pulmonary complications will also be compared. The severity of PPCs scaled by

Clavien-Dindo classification will be treated as an ordinal variable; the ordinal regressions will be conducted. Postoperative length of hospital stay will be analysed using Kaplan-Meier curves and compared with log-rank tests. Cox proportional hazard models were utilized for length-of-stay outcomes, incorporating a shared frailty model. The proportionality assumption was visually inspected using Kaplan-Meier plots, log-log plots, and Schoenfield residuals, with no clear evidence of divergence. Non-parametric comparisons were made using Kaplan-Meier curves and between-group log-rank tests.

For continuous outcomes, linear or quartile regression was chosen based on the skewness of the distribution. Models were adjusted for the ARISCAT index and the time interval from infection to surgery as per randomisation strata, treated as fixed effects. Between-group risk differences were estimated and reported with 95% confidence intervals. Adverse reactions were documented and analyzed, with differences in incidence tested using Fisher exact tests. No Type I error corrections were conducted for multiple tests in this context.

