## Version History

Date (dd-mm-yyyy)	Version	Reason for the update
22-02-2024	1.0	First draft of SAP based on original trial protocol

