## **ABSTRACT**

### **Background**

This a priori statistical analysis Plan describes the analyses for INORDINATE

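### The plan reports a passed proportional-hazards check for length of stay, and names no effect estimate for use if hazards are not proportional

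*SAP*

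**What the plan says.** The Abstract (Background) describes the document's status: "This a priori statistical analysis Plan describes the analyses for INORDINATE". Version History lists only version 1.0, dated 22-02-2024, with the reason "First draft of SAP based on original trial protocol".

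The Secondary Analysis section treats length of stay in two registers. It first plans in the future tense: "Postoperative length of hospital stay will be analysed using Kaplan-Meier curves and compared with log-rank tests". It then moves to the past tense: "Cox proportional hazard models were utilized for length-of-stay outcomes, incorporating a shared frailty model". The next sentence gives the outcome of the model check: "The proportionality assumption was visually inspected using Kaplan-Meier plots, log-log plots, and Schoenfield residuals, with no clear evidence of divergence". Kaplan-Meier and log-rank comparisons are mentioned once more directly afterwards, again without being tied to the result of the check.

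The Scope of the Analysis plan section commits the analyses to strict adherence to the SAP. No other section corrects or explains the reported result.

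**The concern.** A plan should say how an assumption will be checked and what follows from each answer. This one gives the answer. Two things are at stake.

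- **The check has no function.** If the SAP is followed to the letter, proportionality is already settled. An analyst who found crossing hazards would have no instruction on which effect estimate to present. Choosing one at that stage would be a choice made after seeing the data.
- **The sentence conflicts with the document's stated status.** A diagnostic result for this trial cannot exist before its length-of-stay data exist. Either the statement describes data already examined, or it does not describe this trial. It needs correcting in both cases.

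**Working it through.** The plan gives no figure on this point, so the check compares the passages and the dates.

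1. **Is this only loose tense?** Past-tense method wording appears elsewhere in the SAP: in Statistic significance and software (multiplicity), in Sensitivity Analysis (baseline balance), and in Secondary Analysis itself, for example "For continuous outcomes, linear or quartile regression was chosen based on the skewness of the distribution". Such sentences become plans once the tense is changed. The proportionality sentence does so only in part. Its first half becomes a planned inspection, but its last clause, on the absence of divergence, remains a finding in any tense.

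2. **What would the finding require?** Log-log plots and Schoenfeld residuals are computed from observed event times. A check on the treatment effect needs those times by arm. The SAP provides for no such look: Ethics and Study Design and Stopping rules both say that no interim analysis is planned, and Data collection places the database lock after data collection is complete.

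3. **What do the dates allow?** The Background section says: "The trial commenced in February 17, 2023 and the estimated timeline for completion of patient accrual was 12 months". It gives 30 days of participation per patient.
   - Planned end of accrual: 17-02-2023 + 12 months = 17-02-2024.
   - SAP date minus planned end of accrual: 22-02-2024 − 17-02-2024 = 5 days.
   - Last planned follow-up: 17-02-2024 + 30 days = 18-03-2024 (February 2024 has 29 days).
   - Last planned follow-up minus SAP date: 30 − 5 = 25 days.

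   If accrual ran to plan, much of the data would have existed at the SAP date, but follow-up would have had up to 25 days left to run. The dates neither establish nor exclude a look at the data. They are also estimates, since the actual end of accrual is not stated.

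4. **What is available if proportionality fails?**
   - Kaplan-Meier curves need no proportional hazards and would show crossing, but the plan names no summary to be taken from them.
   - The log-rank test remains valid under the null, but it loses power when hazards cross and gives no effect size.
   - The Cox hazard ratio is the only effect estimate clearly attached to the time-to-event analysis, and it is the one that rests on the assumption.
   - The regression options for continuous outcomes are not assigned to length of stay, which the section handles as time-to-event.

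5. **How far does it reach?** Secondary Endpoints lists six items: 30-day mortality, severity of pulmonary complications, unplanned ICU admission, length of stay, thrombotic events and the comprehensive complication index. The Cox model is specified only for length of stay. The Primary Analysis section uses risk ratios, risk differences and binomial models, and the time-to-complication analysis in Sensitivity Analysis uses Kaplan-Meier and log-rank. None of these depends on the sentence.

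**The case against.** The strongest reply is that this is an editing fault with little effect. The section plans Kaplan-Meier curves and log-rank tests unconditionally, so it would be wrong to say that a hazard ratio is all the reader will see whatever the data show. Nor does the text call the hazard ratio the main summary. Length of stay is a secondary outcome, and the SAP treats its uncorrected multiple tests as exploratory. All of this stands, and it limits the point to one missing effect estimate and one sentence that must go.

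A reader might go further and infer that outcome data were examined before the plan was fixed, so that the prespecification of the whole SAP is in doubt. The document does not support that. The model carries a shared frailty term with no cluster defined, in a single-centre trial, which suggests text brought in from another report. Similar tense slips occur where no result is reported. The SAP states that no interim analysis is planned, and on the planned timeline follow-up was incomplete at the SAP date. These features fit carried-over text at least as well as a data look. They do not settle the matter, which is why a short statement from the sponsor is worth asking for.

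Carry-over does not excuse the sentence, because it would then make a statement about this trial that is not true of it.

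**Conclusion.** The point holds, limited to length of stay. The SAP gives the result of a proportional-hazards check in a plan described as a priori. As written, the check cannot alter the analysis, and no effect estimate is named if hazards are not proportional.

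The numerical consequence cannot be given. It depends on how far the discharge hazards depart from proportionality, and the document has no information on that. If they are close to proportional, only the wording is at fault. If they cross, the one named effect estimate would be hard to interpret.

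The conclusion rests on reading the sentence in its plain sense, and on there being no correction elsewhere in the SAP. It does not rest on the dates, and it makes no claim that data were seen. The primary comparison is unaffected. The text should be corrected before analysis, but it does not threaten the trial's main result.

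**What to change.** - Delete the reported result and rewrite the length-of-stay text in the future tense.
- State that proportionality of the treatment effect will be assessed after database lock, using Schoenfeld residuals and log-log plots.
- Keep the Cox hazard ratio. Beside it, report the between-arm difference in restricted mean time to live discharge up to day 30, with its 95% confidence interval. Count in-hospital deaths as not discharged. Say in advance that this difference is the effect estimate relied on if proportionality fails.
- Add one sentence stating whether any outcome data by arm were examined before 22-02-2024.

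The cost is a change of SAP wording and one extra estimate. The downside of that estimate is its fixed horizon: differences in stay beyond day 30 do not contribute. Day 30 matches the trial's last follow-up. Nothing in the primary analysis or the sample size changes.

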### **Secondary Endpoints**

Secondary endpoints include postoperative 30-day all-cause mortality, severity of PPCs scaled by Clavien-Dindo classification, unplanned ICU admission, postoperative length of hospital stay, thrombotic events (including deep venous thrombosis and pulmonary embolism); and postoperative comprehensive complication index (CCI). Details on definition can be found in [the published study protocol \[34\]](#). Other measurements are non-pulmonary complications including stroke, cardiac infarction, ventricular dysfunction, delirium, acute kidney injury, surgical revision for bleeding,

hypotension/hypertension, arrhythmia, hyper-responsiveness.

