### Sample Size Consideration

The sample size for this study has been calculated based on the incidence of postoperative pulmonary complications of incidence of PPCs is reported to be approximately 20% for all surgical populations [62, 63] and increase up to 39.5% after COVID-19 infections[5]. The study assumes a 30% PPC incidence in the control group. We anticipate a 30% relative reduction (from 30% to 20%) in PPCs incidence for the iNO group. At 5% significance level and on consideration of 10% dropouts, the sample size needed to achieve 80% power is thus calculated to be 660 (330 per group) using a

two-sided Chi-squared test with continuity correction.

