### **Baseline and intraoperative Characteristics**

Demographic, baseline, and intraoperative characteristics will be summarised using descriptive statistics and will be presented by treatment group. Categorical variables will be reported as counts and percentages. Percentages will be calculated according to the number of trial participants for whom data are available. Where values are missing, the denominator will be stated and no assumptions or imputations will be made. Continuous variables will be summarized in either means and standard deviation or medians and interquartile range, according to the distribution of the variables.

T-test or Wilcoxon rank sum test will be used for comparison of continuous data.  $\chi^2$  test or Fisher's exact test will be used for comparison of categorical data. Normality for continuous variables will be assessed via the Shapiro-Wilk normality test and visually using QQ-plots and residual plots. Appropriate variable transformation such as natural logarithm will be applied in case of non-normality. Should normality not be obtained through transformation of the

data, alternative non-parametric methods (such as Wilcoxon rank sum test) will be applied. All statistical tests will be 2-tailed with  $p < 0.05$  considered statistically significant. All analyses will be performed on an intention-to-treat basis.

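### The SAP never names a method for the comprehensive complication index. By elimination it falls under a skewness-based choice between mean and quantile regression, with no cut-off, quantile or matching effect measure.

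*SAP*

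**What the plan says.** The SAP lists the comprehensive complication index under Secondary Endpoints. The Secondary Analysis section then assigns methods by type of endpoint:

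- Binary endpoints: Fisher's exact or chi-squared tests.
- PPC severity: "Clavien-Dindo classification will be treated as an ordinal variable; the ordinal regressions will be conducted".
- Length of stay: "Postoperative length of hospital stay will be analysed using Kaplan-Meier curves and compared with log-rank tests", with Cox models in addition.
- Anything else continuous: "For continuous outcomes, linear or quartile regression was chosen based on the skewness of the distribution".

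The index is not mentioned in that section, and the last rule is the only one left for it. Two sentences follow the rule. On covariates: "Models were adjusted for the ARISCAT index and the time interval from infection to surgery as per randomisation strata, treated as fixed effects". On the effect measure: "Between-group risk differences were estimated and reported with 95% confidence intervals".

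A different route for non-normal data stands under Baseline and intraoperative Characteristics: transform first, and if that fails, "alternative non-parametric methods (such as Wilcoxon rank sum test) will be applied".

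**The concern.** A linear model estimates a difference in means and a quantile model a difference at one chosen quantile. These are different questions. The rule lets the shape of the observed data choose between them and gives no threshold that would make the choice reproducible. If the quantile branch is taken, the quantile is not stated: *quartile* may be a slip for quantile, or may mean a particular quartile. A risk difference is the contrast for a yes/no outcome and describes neither model's result.

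For a score with many zeros the gap is more than a matter of labels. If most patients in both arms have no complication and score 0, the median is 0 in both arms. The median contrast then cannot register a treatment effect that a mean or rank comparison of the same data could.

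**Working it through.** **Inputs from the SAP (Sample Size Consideration).** On the placebo rate: "The study assumes a 30% PPC incidence in the control group". The NO rate is 20%, with 330 patients per group and a 10% dropout allowance, so 330 × 0.90 = 297 evaluable per arm. The SAP states no figure for the index, so there is none to reproduce.

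**Assumptions.** A patient without complications scores 0. The SAP does not print the scoring, the share of zeros or an overall complication rate, so a range of rates is shown.

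**Step 1: when does the median leave 0?** PPC-free patients make up 70% (placebo) and 80% (NO). Let x be the share of them with some other complication. The median is at the edge of 0 when (PPC-free share) × (1 − x) = 0.5.

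- Placebo: x = 1 − 0.5/0.70 = 0.286, about 29%.
- NO: x = 1 − 0.5/0.80 = 0.375, about 38%.

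Below these shares the median is expected to be 0 in both arms.

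**Step 2: chance of a zero median in one arm of 297.** The sample median is 0 when at most 148 of 297 scores are non-zero. The exact binomial probability is above 0.9999 at a 30% any-complication rate, 0.9998 at 40%, 0.96 at 45%, 0.50 at 50%, 0.04 at 55% and 0.0002 at 60%.

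**Step 3: both arms together.** Each row is 1000 simulated trials with 297 per arm. Non-zero scores were drawn from eight assumed values between 8.7 and 42.4, with the same distribution in both arms.

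| Any-complication rate, placebo/NO | Median difference = 0 | Upper-quartile difference = 0 | Mean difference | Rank-sum power | Pooled skewness |
|---|---|---|---|---|---|
| 30%/20% | 100% | 4.3% | −1.88 | 80.4% | 1.89 |
| 40%/30% | 100% | 14.0% | −1.87 | 70.4% | 1.37 |
| 45%/35% | 95.5% | 12.9% | −1.87 | 67.4% | 1.16 |
| 50%/40% | 47.1% | 30.9% | −1.88 | 67.5% | 0.99 |
| 55%/45% | 7.9% | 78.0% | −1.78 | 60.8% | 0.84 |
| 60%/50% | 50.0% | 96.3% | −0.31 at the upper quartile; −1.87 in the mean | 59.9% | 0.70 |
| 70%/60% | 65.7% | 94.9% | −0.08 at the upper quartile; −1.84 in the mean | 58.7% | 0.46 |

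In the last two rows the zero median differences return for another reason: both medians tend to sit on the same assumed non-zero score. The high upper-quartile figures from 55%/45% downwards arise in the same way. Both are products of the tied values that were assumed, not of zero scores.

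**Step 4: with the planned adjustment.** Median regression on treatment, ARISCAT class and infection-to-surgery interval was run 60 times per setting.

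- 30%/20% throughout: coefficient 0 in all 60 runs.
- An assumed 30% of patients at high risk with rates 60%/45%, the rest 17%/9% (overall 0.3 × 60 + 0.7 × 17 = 29.9% and 0.3 × 45 + 0.7 × 9 = 19.8%): 0 in all 60 runs.
- High risk 80%/65%, the rest 50%/40%: 0 in one third of the runs.

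**The case against.** Four stronger readings are tempting, and the SAP supports none of them.

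- *The SAP plans median regression.* It says quartile regression and names no quantile. At 30%/20% an upper-quartile difference was 0 in only 4.3% of simulated trials.
- *The difference is fixed at zero.* This needs more than half of each arm to score 0. The only rates in the SAP are for PPCs. The index would also reflect other complications; the SAP lists delirium, acute kidney injury, hypotension/hypertension and arrhythmia without incidences, and cardiac surgery is among the subgroups. The any-complication rate could pass 50%.
- *The skewness rule will select the quantile branch.* Without a cut-off this cannot be known. It is likely if most scores are 0: pooled skewness was 1.89 at 30%/20% under the assumed scores, but only 0.84 at 55%/45%.
- *A real benefit would go unseen.* The primary PPC comparison, ordinal regression of PPC severity, tests of each non-pulmonary complication and the win-ratio analysis would still be available. The SAP also treats multiple tests as exploratory.

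It may also be said that a choice made on pooled skewness, without regard to treatment arm, need not favour either arm. That is fair as far as bias goes, although the SAP does not say that the skewness is to be pooled. It does not answer the point that the quantity being estimated changes with the choice.

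These objections limit the size of the problem. They leave standing the missing cut-off, the missing quantile and the effect measure that fits neither model. The Wilcoxon route in the baseline section does not close the gap, because it stands under another heading and differs from the rule in Secondary Analysis.

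**Conclusion.** The point holds in two parts. Without any outside assumption, the SAP leaves the model, the quantile and the effect measure for a named secondary endpoint to be settled once the data are seen. Conditionally, if complication-free patients score 0 and clearly more than half of each arm is complication-free, a median contrast would be 0 whatever the treatment effect. At the plan's PPC rates taken alone, that happened in every simulated trial, while a rank-sum test on the same data had about 80% power. The condition weakens near a 50% any-complication rate, and at the lower rates the upper quartile is largely unaffected. The rank-sum power and the mean and upper-quartile figures depend on the assumed non-zero scores. The impact is modest, since the endpoint is secondary and exploratory, but the repair is cheap and is sound whatever the share of zeros.

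**What to change.** In Secondary Analysis, name the comprehensive complication index and remove the skewness-based choice for it. Prespecify one analysis: proportional-odds (ordinal) regression of the score on treatment, adjusted for ARISCAT class and infection-to-surgery interval, reporting the common odds ratio with its 95% confidence interval. Add the difference in mean score with a bootstrap 95% confidence interval as a description, and confine the sentence on risk differences to the binary endpoints.

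The cost is SAP wording only; ordinal regression is already planned for PPC severity. The downside is that an odds ratio is less direct than a difference in points, which the descriptive mean difference partly offsets.
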